5.3. INTENTION-TO-TREAT ANALYSIS SET

All subjects who are randomized regardless of treatment adherence or availability of follow-up data will be included in the Intention-to-Treat (ITT) Analysis Set. All analyses of the ITT Analysis Set will be based on each subject's randomized assigned treatment. The ITT analysis set will serve as the primary set for the efficacy analyses.

5.4. PER PROTOCOL ANALYSIS SET

The Per Protocol (PP) Analysis Set will include all subjects in the ITT Analysis Set who meet the study eligibility requirements and have no major protocol deviations that affect the validity of the efficacy measurements. Detailed protocol deviations that may result in subject exclusion from the PP Analysis Set are described in Section 5.5. The PP Analysis Set will serve as the secondary set for efficacy assessment.

5.5. PROTOCOL DEVIATIONS

Protocol deviations will be captured during monitoring visits and recorded in CRF. Deviation will be classified into each of the 9 categories: enrollment criteria, non-compliance, laboratory, dosing, visit schedule, visit/procedure requirement, concomitant medication, informed consent, and other. Date and details of the deviation will be recorded. The list of deviation will be reviewed before unblinding and major protocol deviations that, in the opinion of the medical monitor, will be determined in the ongoing bases. The list of major protocol deviations will be further reviewed before database lock in the unblinded fashion and the deviations that could affect the primary and secondary variables will be determined. Some possible types of major protocol deviations are showing in Table 2.

Table 2 Some Possible Types of Major Protocol Deviations That Lead to Subject or Visit Exclusion from PP analysis set.

Category	Criteria	Exclusion
Inclusion/Exclusion Criteria		
Ineligible subject is enrolled	
 - Subjects not satisfying HbA_{1c} inclusion criteria - Subjects not satisfying eGFR inclusion criteria (inclusion #4 and #7) - Treated with SGLT2 within 3 months of screening 	Subject exclusion
Prior or Concomitant Medication Restrictions		
Use of another SGLT2 inhibitor	Use of an SGLT2 inhibitor, sulfonylurea, or additional metformin as the rescue medication for hyperglycemia	Visit exclusion [exclude data post rescue medication starts]
Randomization/Blinding		
Unblinding	Blind was broken (requested in IWRS)	Visit exclusion [exclude data post blind broken]
Dosing and Compliance		
Dosing Non-Compliance	Subject missed more than 20% of the investigational product doses for the 60 weeks of efficacy assessment period or missed more than 50% between week 48 and week 60	Subject exclusion

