2.2. TIMINGS OF ANALYSES

The final analysis of safety and efficacy is planned after all subjects have completed the 96 weeks of treatment period and a two-week post-dose follow-up period. The treatment assignment is blinded to all study personnel throughout the 96-week treatment and the two-week follow-up periods. The database will be cleaned and locked followed by the unblinding of subject treatment codes.

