3.9.2. Blinding

This is a double-blind, double dummy study. The sponsor, investigators, study coordinators, pharmacists, study subjects, the cardiovascular adjudication committee and the diabetic ketoacidosis committee will be blinded to the study medication.

To maintain blinding of the individual treatment assignment, the results of urinary glucose testing will not be made available to any study personnel or subjects. If knowledge of the test substance is needed to manage a subject's condition, the investigator will contact the IWRS to obtain the treatment assignment. If unblinding occurs for any reason, the time and reason for breaking the blind will be recorded on the case report form (CRF) and the sponsor must be notified within 24 hours.

A designated statistician who is not involved with the study operation will hold the treatment codes. The unblinded treatment information can be provided to the Data and Safety Monitoring Board (DSMB) to facilitate the evaluation of any clinically important increase in the rate of a serious suspected adverse reaction or to the designated safety contact when the treatment information is required to determine if an expedited safety report must be submitted to regulatory agencies.

The treatment assignment will continue to be withheld from the cardiovascular adjudication committee and diabetic ketoacidosis adjudication committee members until all global investigational studies are completed and final analyses to assess cardiovascular and ketoacidosis risks are conducted.

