7.2. SUBJECT ELIGIBILITY AND PROTOCOL DEVIATIONS

All subjects, including screen failure subjects, who violate the Inclusion/exclusion criteria will be listed. Reason for screen failure will be summarized.

Deviations that could affect the primary and secondary variables will be considered when determining a subject's eligibility for the PP population. The number and percent of subjects who had any major deviation and each type of major protocol deviation will be tabulated for the ITT Analysis Set. All deviation term and class will be listed.

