9.3.3. AE of Special Interest

AE of special interest include UTI, pyelonephritis urosepsis, GMI, diuretic effects including hypovolemia, hypotension episodes, hypoglycemia, hepatotoxicity, MACE, fractures, malignancies, hypersensitivity reactions, acid-base disorders including diabetic ketoacidosis, rash, and renal failure events. These AEs of special interest, except for cardiovascular events and amputations, will be prospectively identified based on the MedDRA PTs in the AEs log by a medical expert prior to the data base lock and unblinding of the individual subject treatment assignment. The list of AEs of special interest will be confirmed in a peer review process. Cardiovascular events, hypoglycemia events by severity, and amputations will be summarized separately.

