12. DATA AND SAFETY MONITORING BOARD

An independent data and safety monitoring board (DSMB) will review descriptive summaries of accumulating safety, subject disposition and limited efficacy data every 6 months, or a frequency recommended by the DSMB.

A designated statistician who is not involved with the study operation will hold the treatment codes. The unblinded treatment information can be provided to the DSMB to facilitate the evaluation of any clinically important increase in the rate of a serious suspected adverse reaction or to the designated safety contact when the treatment information is required to determine if an expedited safety report must be submitted to regulatory agencies. The data outputs for this review will be created by an unblinded team. Personnel involved in the conduct of the study will not participate in the preparation of these outputs, receive the data, or participate in the unblinded portions of the DSMB meetings. More details will be provided for DSMB charter and DSMB SAP.

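### SAP 5.5 has the final review of major protocol deviations done unblinded before database lock, which contradicts SAP 2.2 and lets per-protocol exclusions be settled with treatment known

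*SAP*

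**What the plan says.** SAP 5.5 describes two reviews of protocol deviations. In the first, "The list of deviation will be reviewed before unblinding", and the medical monitor identifies major deviations on an ongoing basis. In the second, "The list of major protocol deviations will be further reviewed before database lock in the unblinded fashion", and this step settles which deviations could affect the primary and secondary variables. SAP Table 2 then lists deviations that lead to subject or visit exclusion from the PP set, but offers them as examples, not as a complete list.

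SAP 7.2 links the second review to the analysis set: "Deviations that could affect the primary and secondary variables will be considered when determining a subject's eligibility for the PP population".

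On timing, SAP 2.2 states: "The database will be cleaned and locked followed by the unblinding of subject treatment codes". It also states: "The treatment assignment is blinded to all study personnel throughout the 96-week treatment and the two-week follow-up periods". Protocol 9.3.3 places PP assignment before database lock and leaves the detail of excluding deviations to the SAP. Protocol 9.11 mentions lock and then unblinding, so its order is implied only.

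**The concern.** A per-protocol set protects against bias only if its membership is fixed by people who do not know who received which treatment. As worded, SAP 5.5 places the last decision about which deviations matter after unblinding and before lock. That cannot be reconciled with a plan in which lock comes first.

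The analyses at stake are the supportive PP analysis of HbA1c at week 60 (SAP 8.1.1) and the PP repeats of the secondary endpoints (SAP 8.2). PP is the secondary set and ITT the primary one (SAP 5.3 and 5.4). In a non-inferiority trial the PP result still carries weight: Protocol 9.5.2 treats the conclusion as more robust when ITT and PP agree. That agreement is worth less if PP membership could have been set with the codes known.

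**Working it through.** **1. The passages side by side**

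| Source | Step | Timing and blinding |
|---|---|---|
| SAP 5.5, first review | Deviation list reviewed | Before unblinding |
| SAP 5.5, second review | Major deviations that could affect endpoints determined | Before lock, unblinded |
| SAP 7.2 | Those deviations considered for PP eligibility | Follows from SAP 5.5 |
| SAP 2.2 | Lock, then codes released | Unblinding after lock |
| Protocol 9.3.3 | PP assignment | Before lock |
| SAP 9.3.3 | Classification of adverse events of special interest | Before lock and before unblinding |

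The second row conflicts with the SAP 2.2 row. Protocol 9.3.3 is not a separate contradiction: it gives timing only, and under SAP 2.2 that timing means blinded.

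**2. Does another section make the sentence workable?** No.
- SAP 3.9.2: "A designated statistician who is not involved with the study operation will hold the treatment codes". The DSMB and the safety contact are named as recipients for safety purposes, and an investigator can obtain a code to manage a subject. Deviation reviewers are not named.
- SAP 12 describes an unblinded team, but only for DSMB outputs: "Personnel involved in the conduct of the study will not participate in the preparation of these outputs, receive the data".
- SAP 13, which lists changes from the protocol, does not mention an unblinded deviation review.
- The closest comparable task, in SAP 9.3.3, is done "by a medical expert prior to the data base lock and unblinding of the individual subject treatment assignment".

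**3. The plan's own sample size (background for step 4)**

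Inputs from SAP 3.8: margin 0.35, SD 1.0, one-sided alpha 0.025, power 90%, dropout 18%.

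n per arm = 2 × (1.960 + 1.282)² × 1.0² / 0.35² = 171.6, so 172. Then 172 / 0.82 = 209.8, so 210. Both figures reproduce.

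**4. Size of the possible effect on the PP test**

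The setting was 172 per arm, normal outcomes, SD 1.0 and a true difference equal to the margin (0.35). Non-inferiority is met when the upper 95% t limit is below 0.35. Each scenario used 60,000 simulated trials (simulation SE 0.06 to 0.09 percentage points). The pool of excludable subjects, m, is an assumption: 5% or 10% of 172, giving 9 or 17.

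| Scenario | m | One-sided error | Mean shift (% HbA1c) | 95% CI half-width |
|---|---|---|---|---|
| No exclusion | 0 | 2.43% | – | 0.212 |
| Treatment known, outcome unused, whole pool removed from bexagliflozin arm | 9 | 2.40% | 0.00003 | 0.215 |
| Same | 17 | 2.47% | 0.00003 | 0.218 |
| Treatment known, outcome unused, random half of pool removed from bexagliflozin arm | 9 / 17 | 2.42% / 2.46% | at most 0.0001 in size | – |
| Whole pool removed from both arms | 9 / 17 | 2.48% / 2.48% | – | – |
| Treatment and outcome both used, pool members above the bexagliflozin arm mean removed | 9 | 3.87% | -0.021 | – |
| Same | 17 | 5.67% | -0.041 | – |

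Closed-form check of the selective shift. About half the pool lies above the mean, with average excess √(2/π) = 0.798 SD, so shift = -(m/2) × 0.798 / (172 - m/2).
- m = 9: -4.5 × 0.798 / 167.5 = -0.021
- m = 17: -8.5 × 0.798 / 163.5 = -0.041

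Both agree with the simulation.

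**The case against.** The strongest reply is that this is a drafting slip with no practical route to harm. The first review in SAP 5.5 is before unblinding, SAP 2.2 unblinds after lock, the comparable adverse-event step is blind, and no section gives deviation reviewers access to the codes. The second review only sorts deviations already classed as major, and the criteria printed in Table 2 are largely objective. The SAP 2.2 statement about blinded personnel covers treatment and follow-up, not the gap between last follow-up and lock, so the direct conflict is one sentence against one sentence. SAP 7.2 says the deviations are considered in determining PP eligibility, not that they decide it alone. Finally, PP is supportive, and the error figures above the nominal level depend on outcome-driven removal that the SAP does not describe.

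Much of this stands. The word probably is a slip, the room for judgement is limited, and the 3.9% and 5.7% figures are hypothetical. It does not remove the problem. The sentence reads naturally as a deliberate second stage and a team could follow it. Because Table 2 gives examples only, deciding which other major deviations could affect the endpoints remains a judgement. By a pre-lock review the week 60 HbA1c values will have been collected, and the documents do not say that they are withheld from the reviewer.

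**Conclusion.** The point holds. SAP 5.5 is wrong as written: it calls for an unblinded review before lock, the review feeds PP eligibility, and this contradicts the lock-then-unblind order in SAP 2.2.

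The consequence is the loss of a safeguard, not demonstrated bias. Under the step 4 model, knowing treatment without using outcome leaves the PP error essentially unchanged, provided deviations are unrelated to outcome; the interval is slightly wider. Inflation requires selection on both treatment and outcome. The pool sizes are assumed and do not come from the documents.

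The ITT non-inferiority conclusion and the testing of the secondary endpoints do not depend on this step. Confidence is high for the inconsistency itself. The correction should be made before any codes are released, because an ambiguity over who knew what cannot be repaired afterwards.

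**What to change.** In SAP 5.5, change the second review so that it is carried out in a blinded fashion. Add a sentence stating that the final PP subject and visit exclusions, including any outside Table 2, are determined and documented by blinded staff before database lock and before the treatment codes are released.

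The cost is one or two sentences. SAP 5.5 already provides for a review before unblinding, so no new step, data or analysis is needed.

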6. GENERAL ASPECTS FOR STATISTICAL ANALYSIS

6.1. GENERAL METHODS

Statistical methodology and analyses are in accordance with the principles outlined by the ICH E9 guidelines. All statistical analyses will be conducted using SAS statistical software version 9.3 or higher.

Tables, listings and figures (TLFs) will be produced in accordance with the principles outlined by the ICH E3 guidelines. For most summary statistics, data will be analyzed by the following treatment groups: Bexagliflozin 20 mg; Glimepiride; and total of all treatment groups.

Data summaries will use descriptive statistics (number of subjects [n], mean, standard deviation [SD], Q1, median, Q3, minimum, and maximum) for continuous variables, and frequency and percentage of subjects for categorical and ordinal variables, unless otherwise specified.

All confidence intervals (CIs) will be two-sided 95% CIs.

The analysis visit window will be assigned to data collection. One selected data point per visit will appear in summary tables and figures. Refer to section 6.4 for details. All visit assessment data will be included in shift tables and appear in the subject listings.

No data imputation will be applied for missing values, unless otherwise specified.

6.2. KEY DEFINITIONS

6.2.1. Baseline Values

For subject who is dosed, baseline is defined as the last non-missing value on or prior to the first dose of double-blind study medication. For subject who is not dosed, baseline is defined as the last non-missing value on or prior to the randomization date.

6.2.2. First Dose Date

Two “first dose dates” will be required, one for the Run-In period and one for the double-blind treatment period. The first dose date for the Run-In period will be the date of administration of the first dose of single-blind placebo tablets during the Run-In period. The first dose date for the double-blind treatment period will be the date that the first dose of randomized, double-blind study drug is administered. Both first dose

dates will be obtained from the CRF. Study analyses will use the double-blind treatment period first dose date.

6.2.3. Study Day

Study Day is the number of days starting from the first administration of double-blind study drug, which is counted as Study Day 1. If the assessment date is after the date of the first double-blind medication, the study day is calculated as date of assessment - date of the first dose administration+1. If the assessment date is prior to the date of the first double-blind medication, the study day is calculated as date of assessment - date of the first dose administration.

6.2.4. Duration

Duration of double-blind treatment will be determined as Double-Blind Duration = Double-Blind Last Dose Date - Double-Blind First Dose Date plus 1. Duration of Run-In period will be determined as Last Dose Date in the run-in period minus First Dose Date in the run-in period plus 1.

6.2.5. End of Study

The end of study is defined as the date of final contact as entered on the End-of-Study page of the CRF.

6.2.6. Patient Years

Patient years are calculated as sum of the duration from first dose of double-blind treatment to the end of study / 365.25 of all subjects in the specified analysis set and treatment arm. This is used as the denominator of the computation of incidence rate.

6.3. MISSING DATA

The handling of missing or incomplete data is described for each endpoint and data type (as needed) in Sections 7 to 10.

6.4. ANALYSIS VISIT WINDOWS

Table 3 shows how data will be mapped to analysis visits prior to selection of records for analysis. All post-baseline visits, including unscheduled and early termination visits, will be mapped. After mapping the data to the analysis visits, the following rules will apply unless other handling is specified for a particular analysis.

- If multiple records are available within a single analysis visit window, the record closest to the planned assessment day will be selected for analysis.

- If 2 records are equidistant from the target day, then the later record will be selected.
- If a subject has no record in an analysis window, the subject will be considered missing at that visit.

Table 3 Analysis Visit Windows

Data type	Study Day Window	Scheduled day	Scheduled Visit/Week
Body Weight, HbA _{1c} , Fasting Plasma Glucose, Lab data (including Lipids), EQ-5D-3L	Day 2 - 63	Day 42	Visit 9/Week 6
	Day 64 - 125	Day 84	Visit 10/Week 12
	Day 126 - 209	Day 168	Visit 11/Week 24
	Day 210 - 293	Day 252	Visit 12/Week 36
	Day 294 - 377	Day 336	Visit 13/Week 48
	Day 378 - 461	Day 420	Visit 14/Week 60
	Day 462 - 587	Day 504	Visit 15/Week 72
	> 587	Day 672	Visit 17/Week 96
Vital signs (except for height and weight)	Day 2 - 21	Day 14	Visit 7/Week 2
	Day 22 - 35	Day 28	Visit 8/Week 4
	Day 36 - 63	Day 42	Visit 9/Week 6
	Day 64 - 125	Day 84	Visit 10/Week 12
	Day 126 - 209	Day 168	Visit 11/Week 24
	Day 210 - 293	Day 252	Visit 12/Week 36
	Day 294 - 377	Day 336	Visit 13/Week 48
	Day 378 - 461	Day 420	Visit 14/Week 60
	Day 462 - 587	Day 504	Visit 15/Week 72
	> 587	Day 672	Visit 17/Week 96
ECG	Day 2 - 294	Day 168	Visit 11/Week 24
	Day 295 - 546	Day 420	Visit 14/Week 60
	> 546	Day 672	Visit 17/Week 96

* Week 96 is the end of treatment visit for those subjects completing the study per protocol. For endpoint of lab and vital sign, the first collection after assigned Week 96 and > 7 days from Week 96 visit will be considered as Week 98 visit.

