3.3.3.2 Treatment Period

During the treatment period, subjects will be advised to continue daily, fasting SMBG measurements. Subjects should contact the clinic if any fasting SMBG is ≥ 270 mg/dL (15 mmol/L) from week baseline to week 6, ≥ 240 mg/dL (13.3 mmol/L) after week 6 to week 12, or ≥ 200 mg/dL (11.1 mmol/L) after week 12. Blood glucose values collected via SMBG will be evaluated at study visits by the investigator. In addition, hyperglycemia will be monitored by FPG at scheduled visits.

If hyperglycemia is identified through SMBG or FPG measurements, the investigator will determine whether the subject has fasted for a minimum of 10 h prior to the morning blood draw to ensure that the SMBG or FPG value is truly a fasting sample. If proper fasting has not occurred, the subject will be asked to return for a repeat blood test within a week.

During the treatment period, hyperglycemia should be managed first with diet and exercise counseling. If hyperglycemia continues after diet and exercise counseling, the investigator should intensify medical therapy if it is necessary for the well-being of the subject. Options for intensification of medical therapy will vary during the study, including up-titration of glimepiride dose (weeks 0-6) and addition of rescue medication (see below, *Intensification of Medical Therapy for Hyperglycemia*).

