6.9.2 Sample Collection, Storage, and Shipping

6.9.2.1 Hematology, Blood Chemistry, Serum Lipids, and Glycemic Control Assessments

Blood samples for hematology, chemistry, serum lipids and glycemic control assessments will be collected. Subjects will be in a seated or supine position during blood collection. Samples will be collected at the time points indicated in the schedule of events in [Appendix 1](#) and [Appendix 2](#).

The study staff will contact each subject prior to a scheduled clinic visit to confirm the time of the visit and to remind the subject of proper fasting practice. A subject must be queried to assess compliance with an approximately 10 h fast prior to blood draw to ensure the FPG and triglycerides values can be accurately determined. If a subject has not fasted for approximately 10 h, the subject must return as soon as can be arranged (within 1 week) to provide a specimen after proper fasting.

Low-density lipoprotein-cholesterol (LDL-C) will be calculated by the Friedewald equation. If triglycerides are > 400 mg/dL, the calculated LDL-C value is invalid by this equation and will be set as missing. Direct LDL-C will be determined in subjects whose triglycerides are > 350 mg/dL at screening visit. All subsequent LDL-C of these subjects will be determined by the same direct LDL-C measurements only.

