7 STUDY ACTIVITIES

The study activities at each clinic visit listed below are presented in [Appendix 1](#). The required laboratory tests scheduled at each visit are listed in [Appendix 2](#). Detailed study procedures are described in [Section 6](#).

A visit window of ± 3 days is allowed for all visits except Visit V6. Visit V6 is the day of randomization and is the basis for all subsequent visit windows.

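### When a non-fasted glucose sample and its fasting repeat fall in one analysis window, SAP 6.4 chooses by date alone and would usually keep the non-fasted value

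*SAP*

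**What the plan says.** SAP 6.4 assigns every post-baseline record to a window: "All post-baseline visits, including unscheduled and early termination visits, will be mapped". Table 3 lists FPG and laboratory data, including lipids, under this scheme. The selection rule is: "If multiple records are available within a single analysis visit window, the record closest to the planned assessment day will be selected for analysis". On ties, "If 2 records are equidistant from the target day, then the later record will be selected". The section leaves room for exceptions, since "the following rules will apply unless other handling is specified for a particular analysis". None concerning fasting appears in SAP 8.3.1 (FPG) or SAP 9.4 (laboratory evaluations).

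The protocol provides for a second sample in two places. Section 3.3.3.2 has the investigator check fasting once hyperglycemia has been seen on self-monitoring or FPG: "If proper fasting has not occurred, the subject will be asked to return for a repeat blood test within a week". Section 6.9.2.1 says that a subject who has not fasted for about 10 hours must come back: "the subject must return as soon as can be arranged (within 1 week) to provide a specimen after proper fasting". SAP 3.11 and 9.4 repeat this second requirement and give its purpose, which is accurate FPG and triglyceride values. Neither says that the later specimen is the one to analyse.

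The protocol also restricts the draw itself. Section 3.3.2 requires the fast to be confirmed beforehand, and the laboratory visits in Section 7 make the draw conditional on a completed 10-hour fast.

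**The concern.** A repeat ordered because the first sample was not fasting is the valid measurement for that visit. A rule that looks only at dates will tend to prefer the first sample, because that one was taken at the scheduled visit and the repeat comes days later. The subject is recalled for a valid specimen, and the by-visit analysis then uses the invalid one.

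The repeat is not lost altogether: SAP 6.1 keeps all visit data in shift tables and listings. It would be missing from the by-visit FPG summaries and from the repeated-measures model in SAP 8.3.1. Triglycerides fall under the same rule and also need the fast. The baseline rule in SAP 6.2.1 works the other way. It takes the last value up to the first dose, so a fasting repeat obtained in time would replace a non-fasted baseline sample. Change from baseline could then set a fasting baseline against a non-fasted follow-up.

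**Working it through.** The plan gives no figure on this point, so there is none to reproduce.

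**Inputs**
- First-draw offset from the target day, *d*: -3 to +3, from protocol Section 7 ("A visit window of ± 3 days is allowed for all visits except Visit V6").
- Lag from first draw to repeat, *r*: 1 to 7 days, from the one-week limit in protocol 3.3.3.2 and 6.9.2.1.
- Selection and tie rules: SAP 6.4.
- Equal weight for all 7 × 7 = 49 combinations: an assumption. The documents give no distribution for either quantity.

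**Rule.** The non-fasted first draw is kept when its distance from the target day is strictly smaller than that of the repeat, that is, abs(*d*) < abs(*d* + *r*). A tie goes to the repeat.

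**Count, visits centred on the target day**
- *d* = 0, 1, 2, 3: the repeat is always further away, so the first draw is kept in 4 × 7 = 28.
- *d* = -1: kept when *r* is 3 or more, 5 combinations.
- *d* = -2: kept when *r* is 5 or more, 3 combinations.
- *d* = -3: kept only when *r* is 7, 1 combination.
- Total: 28 + 5 + 3 + 1 = 37, and 37/49 = 75.5%.

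**Count, visits one day late.** SAP 6.2.3 makes the first dose Study Day 1. A visit exactly 42 days after randomization, with dosing on the same day, is therefore Day 43 against a target of Day 42. With offsets of -2 to +4 the count is 5 × 7 + 5 + 3 = 43, and 43/49 = 87.8%.

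**By repeat lag (share of the 7 offsets in which the non-fasted draw is kept)**

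| Repeat lag | Centred | One day late |
|---|---|---|
| 1 or 2 days | 4/7 = 57% | 5/7 = 71% |
| 3 or 4 days | 5/7 = 71% | 6/7 = 86% |
| 5 or 6 days | 6/7 = 86% | 7/7 = 100% |
| 7 days | 7/7 = 100% | 7/7 = 100% |

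**Do both records share a window?** The latest repeat is at target + 1 + 3 + 7 = target + 11 days, and the earliest first draw is at target - 3. For Week 6 that is Day 53 against an upper limit of Day 63, and Day 39 against a lower limit of Day 2. For Week 60 it is Day 431 against Day 461, and Day 417 against Day 378. Every window from Week 6 to Week 72 contains both records.

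**After the change.** If the non-fasted record is set aside whenever a fasting one is present, the fasting repeat is selected in 49 of 49 combinations.

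**The case against.** The strongest reply is that the pair should not arise. If protocol 3.3.2 and Section 7 are followed, a non-fasted subject is not drawn. Section 6.9.2.1 then describes a postponed first specimen rather than a repeat. Section 3.3.3.2 is narrow as well: when self-monitoring raised the alarm, there need be no laboratory FPG to compete with the repeat. What remains is a high laboratory FPG drawn without a proper fast despite the restriction, or some other draw made against it. This reply stands as to frequency. It does not remove the gap, because Section 3.3.3.2 provides for an FPG found after the event not to be fasting, and the SAP then selects the wrong record more often than not.

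A reader might infer three stronger things, none of which the documents support:
- **That non-fasted values are routinely analysed as FPG.** The draw restriction points the other way. The 76% is conditional on both records existing.
- **That mean FPG is shifted by a definite amount.** This needs the share of visits with such a pair and the excess of a non-fasted value over a fasting one. The documents give neither.
- **That one arm is affected more.** The trial is double-blind, the fasting procedure is the same in both arms, and nothing in the documents shows a difference in non-fasted draws.

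Two further reservations hold. Section 6.9.2.1 asks for the return visit as soon as it can be arranged, which favours short lags and the lower figures in the table. The SAP's shells and appendix are separate attachments and were not available, so handling specified there cannot be excluded.

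**Conclusion.** The point holds in conditional form and is minor. Given a non-fasted sample and a fasting repeat in one window, SAP 6.4 keeps the non-fasted value in about 76% of equally weighted combinations. The figure is 57% for repeats within 1 to 2 days and 88% overall if visits run one day late under the Day 1 convention. These percentages rest on the ±3-day visit window, the one-week limit and equal weighting. How often such pairs occur is unknown, and it should be low if the fasting restriction is observed.

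The reach is limited. FPG over time is exploratory under protocol 2.3 and SAP 8.3, with nominal p-values and no multiplicity adjustment. Triglycerides appear only in descriptive laboratory summaries. The primary HbA1c analysis, the key secondary tests on weight, systolic pressure and hypoglycemia, the type I error and the sample size are all unaffected.

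**What to change.** Add to SAP 6.4 that, for FPG and triglycerides, a record identified as non-fasted is not eligible for selection when a fasting record exists in the same window, and that the nearest-day and tie rules then apply among the fasting records. Leave HbA1c selection as it is.

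The sponsor should confirm that fasting status at each draw reaches the database. Sites must ask about it under protocol 6.9.2.1, but neither document says that the answer is recorded as data, and without it the rule cannot be programmed.

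The cost is one sentence in the SAP plus that check. Worded this way, no visit loses its value. If the sponsor also chose to exclude non-fasted records that have no fasting counterpart, a few FPG or triglyceride values would become missing. Settling this before unblinding avoids a choice between records after results are known.
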